 - H1.* Eighteen sessions (6-8 weeks) of gait training comprising fast treadmill walking and functional electrical stimulation (FastFES) will result in Improvements in gait biomechanics, corticospinal excitability, and walking function.
 - H2.* Improvements in gait biomechanics will precede the improvements in corticospinal excitability and walking function.
 - H3.* Improvements in walking function will be correlated to improvements in corticospinal excitability.
- By utilizing data collected on cohort 2 of subjects who receive different rehabilitation strategies during each training session, we will analyze short-term changes induced by 1-3 sessions of gait retraining to test the following hypothesis:
 - H4.* The magnitude of improvements in gait biomechanics and corticospinal excitability will be greater for gait training sessions that comprise:
 - walking at a faster versus slower speed
 - walking with versus without FES, i.e. Fast versus FastFES
 - walking with FES delivered to two versus one muscle during gait
 - walking with 2 belts going at different speeds or directions versus regular treadmill walking
 - walking with versus without visual bio-feedback or other feedback (e.g. verbal, tactile) about targeted parameters during gait
 - greater dosages (# of walking steps per session) of walking practice
 - combination of 2 strategies versus a single rehabilitation strategy

5. Study design and methods

Research Procedures

Flowchart showing the overview of study procedures.

The overall goal of this protocol is to provide novel insights into the biomechanical and neural mechanisms underlying gait rehabilitation. To achieve this goal, a series of experiments will be performed on young able-bodied individuals as well as stroke survivors. The protocols to be tested and procedures to be used are described in detail here. For all the procedures and sessions described below, all testing procedures will be explained to the subject at the beginning of each testing session. Also,

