Hypotheses testing will be done with a p-value set at 0.05. The outcome variables used for analyses will include peak knee and ankle flexion during walking, propulsive forces during walking, walking speed and endurance, peak and duration of EMG activation during walking, and TMS-derived measures of corticospinal excitability (peak EMG in response to TMS, motor threshold intensity, slope and peak of the TMS-recruitment curve). To test *H1*, for each of the variables, one-way repeated measures ANOVA will be performed to check for differences in the variable after versus before 18 sessions of training. To test *H2*, we will plot the dependent variable versus time (test session number). Using these plots, the time to plateau and the time when the variable first shows a positive within-session change (threshold time) will be determined. One way repeated measures ANOVA will be used to compare the time to plateau and threshold time among 3 variables – peak propulsion, peak TMS muscle response, and over ground walking speed. To test *H3*, a Pearson's correlation will be performed between the change in peak propulsion after training versus change in peak TMS muscle response after training. For the hypothesis involving within-session changes (*H4*), repeated measures ANOVA will be performed to compare the within-session percentage change for each variable between different rehabilitation strategies.

Power Analysis: The current protocol has been powered using the primary outcome measure of paretic propulsive force generation. Based on means and standard deviations from our existing pilot data, for each aim, a sample of 24 subjects will provide 80% power to detect a 4.2% difference in propulsive force between sessions with standard deviation of 6% at a two-sided alpha level of 0.05. After completion, the data from this study will be used to conduct systematic power analysis for other outcome variables, which will be utilized to design a larger-scale future study.

8. Adverse event reporting

We will notify the IRB of any adverse events that occur during the protocol.

10. Device information

Equipment for Motion Analysis and Gait Retraining: A 7-camera system will be used to collect motion analysis data (Vicon, Oxford, UK). Ground reaction forces during treadmill walking will be collected using a treadmill instrumented with two 6-component force platforms under each

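### H1 and H4 are tested on every variable and contrast at an unadjusted 0.05, and the named primary outcome decides neither hypothesis

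*Combined protocol and SAP*

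**What the plan says.** Section 7 gives one level for all testing: "Hypotheses testing will be done with a p-value set at 0.05". Its outcome list has seven gait and function variables, "peak knee and ankle flexion during walking, propulsive forces during walking, walking speed and endurance, peak and duration of EMG activation during walking", and four TMS measures, "peak EMG in response to TMS, motor threshold intensity, slope and peak of the TMS-recruitment curve". That makes 11, and the list is worded so that more could be added.

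- **H1.** Section 7: "for each of the variables, one-way repeated measures ANOVA will be performed to check for differences in the variable after versus before 18 sessions". In Section 4 the hypothesis is that training "will result in Improvements in gait biomechanics, corticospinal excitability, and walking function".
- **H4.** Section 7: "repeated measures ANOVA will be performed to compare the within-session percentage change for each variable between different rehabilitation strategies". Section 4 states "The magnitude of improvements in gait biomechanics and corticospinal excitability will be greater for gait training sessions that comprise" and then lists seven contrasts: speed, FES, number of muscles stimulated, split-belt, feedback, dose, and combination. Section 5 refers to the first two as separate hypotheses, 4a and 4b.
- **Primary outcome.** The power paragraph of Section 7: "The current protocol has been powered using the primary outcome measure of paretic propulsive force generation". It gives 24 subjects for each aim, 80% power, a difference of 4.2%, an SD of 6% and a two-sided alpha of 0.05.

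The document gives no multiplicity adjustment, no testing order, and no rule on which or how many variables must be significant for H1 or H4 to count as supported.

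**The concern.** The study is sized on one outcome at an undivided 0.05, yet for H1 and H4 that outcome is one of 11 equals. Suppose propulsion shows nothing and one TMS measure reaches p = 0.04. Nothing in the plan says whether H1 is then supported. A claim of support for either hypothesis therefore has no known error rate.

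This also bears on later work. Section 5 says that the Cohort 1 and 4b data will feed the methods, planning and sample size of a larger trial, and Section 7 says that the data will be used for power calculations on other outcomes. If such calculations leaned on effects noticed because they crossed 0.05, those effects would tend to be overestimates.

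**Working it through.** **1. The plan's own figure.** The standardised effect is 4.2/6 = 0.70. Taking 6% as the SD of the paired difference, the normal formula gives ((1.960 + 0.842)/0.70)² = 16.02, so 17 subjects; the paired t test needs 19. At n = 24 the paired t test has 90.7% power. The stated 24 at 80% is recovered if 6% is a single-session SD with a within-subject correlation of about 0.31, which the document does not state. That is a separate matter. What counts here is that the calculation uses 0.05 undivided, on one outcome.

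**2. Number of tests (Sections 4 and 7).**
- H1: 7 + 4 = 11.
- H4, all variables in all contrasts: 7 × 11 = 77.
- H4, only the biomechanics and corticospinal variables that its wording names (11 less walking speed and endurance): 7 × 9 = 63.
- H4, one omnibus ANOVA for each variable: 11.

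**3. Chance of at least one p < 0.05 with no true effect, independent tests:** 1 − 0.95^m. The expected number of false positives is 0.05m.

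| Family | m | At least one | Expected |
|---|---|---|---|
| H1 | 11 | 43.1% | 0.55 |
| H4, omnibus for each variable | 11 | 43.1% | 0.55 |
| H4, named domains only | 63 | 96.1% | 3.15 |
| H4, all variables and contrasts | 77 | 98.1% | 3.85 |

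Limiting the omnibus reading to the nine named variables gives 37.0%.

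**4. Correlated tests.** The document gives no correlations, so these are assumed. The figures come from simulated equicorrelated one-sample t tests with n = 24.

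| Correlation | H1, 11 tests | H4, 77 tests |
|---|---|---|
| 0.3 | 38% | 90% |
| 0.5 | 31% | 74% |
| 0.8 | 19% | 35% |

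**5. Favourable direction only.** Both hypotheses predict improvement, so a significant worsening supports neither. With 0.025 for each independent test, H1 gives 1 − 0.975^11 = 24.3%, and H4 with 77 tests gives 1 − 0.975^77 = 85.8%.

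**6. A conjunctive reading of H1.** Suppose H1 needed at least one significant variable in each of its three domains (5 gait and EMG, 4 TMS, 2 function). Under independence the rate is (1 − 0.95^5)(1 − 0.95^4)(1 − 0.95^2) = 0.226 × 0.185 × 0.0975, about 0.4%. Positive correlation would raise it.

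**The case against.** The strongest reply is that this is an early, non-randomised study meant to lay groundwork, and that strict error control is partly a matter of taste. That argues for a light remedy, and the one below is light. It does not remove the gap, because Sections 4 and 7 present H1 and H4 as directional hypotheses tested at 0.05 and do not label the non-primary outcomes exploratory.

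A second reply is that H1 joins its three domains with an *and*, so it may require all three to improve. Step 6 shows that such a rule would limit the inflation. The document does not state it.

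Three stronger readings are tempting and are not supported:

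- *Propulsion has no role in the analysis.* Section 7 uses peak propulsion among the three variables compared for H2 and as one of the two correlated for H3. The gap concerns H1 and H4.
- *Chance findings will choose the strategies and outcomes of the larger trial.* Section 5 speaks of methods, planning and sample size, and names only Cohort 1 and 4b. Nothing says that anything will be selected by p < 0.05.
- *The error rates are 43% and 98%.* These assume independent, two-sided tests and that any one result suffices; the 98% also needs all 77 tests to be run separately. Some outcomes are plainly related, such as the peak EMG response to TMS and the peak of the recruitment curve.

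**Conclusion.** The concern holds for H1 and H4. As written, Section 7 does not say which result decides either hypothesis. If one significant variable is enough, the false-positive rate is well above 5% in every case computed on that basis:

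- **H1:** 43% if independent, about 19% to 38% at assumed correlations of 0.8 to 0.3, and 24% counting only favourable independent results.
- **H4:** 43% with one omnibus test for each of 11 variables and 96% to 98% with 63 to 77 separate tests, all independent; about 35% to 90% for 77 tests at correlations of 0.8 to 0.3; and 86% for 77 independent tests counting only favourable results.

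All these figures assume no true effect on any variable. A stated rule requiring every H1 domain to improve would change the H1 conclusion. The point should be settled before analysis; it does not undermine the design.

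**What to change.** In Section 7, state that:

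1. Paretic propulsive force, tested at two-sided 0.05, decides H1.
2. For H4, the same outcome at two-sided 0.05 decides the FastFES versus Fast contrast (4b), the one H4 contrast that Section 5 singles out for planning.
3. All other variables and contrasts are secondary or exploratory. Either control the false discovery rate within each hypothesis, or report estimates with 95% confidence intervals and no significance claim.

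One contrast has to be named because propulsion tested alone across all seven still gives 1 − 0.95^7 = 30.2% if independent. The 0.05 applies to each hypothesis separately and not to H1 and 4b jointly.

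**Cost.** The change is a few sentences, with no added subjects or procedures. H1 and 4b keep their full power on propulsion. The change is not free elsewhere: the power statement covers each aim, so it plausibly includes propulsion in the other six H4 contrasts, and those lose some power or their significance claim. Fewer secondary results will be nominally significant.

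For comparison, taking 6% as the SD of the paired difference, Bonferroni over the seven contrasts (0.05/7 = 0.0071) would cut power on propulsion at n = 24 from 90.7% to 68.0% and need 30 subjects for 80%. Over the 11 H1 variables (0.05/11 = 0.0045), power would be 61.5%, with 32 subjects needed for 80%.

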For gait training, as part of Cohort 1, the subject will receive the same type of walking training (fast treadmill walking with electrical stimulation) for all 18 sessions and participate in 2-3 training sessions per week over the course of 6-weeks. For cohort 1, the gait training sessions may comprise up to six 6-minute bouts of walking with rest breaks between bouts (total 30-minutes of walking). The last training bout (bout 6) may comprise 6-minutes of over ground walking (Fig. 1), during which subjects will be asked to walk as fast as they can. For safety, a physical therapist will walk with and guard the subject during over ground walking. For cohort 1, outcome measures may be obtained before, after, and intermittently throughout the 6-weeks of training (e.g. clinical testing, muscle strength testing, and assessment of corticospinal and spinal excitability).

Subjects in Cohort 2 will receive different types of walking training (e.g. treadmill walking at slow or fast speed, training with (FastFES) or without stimulation (Fast), training with or without feedback, etc.) for each of the training sessions, and will complete 1-3 training session per week with a variable delay (1-day to several weeks) between consecutive sessions. For cohort 2, outcome measures may be obtained before, after, and intermittently during each of the training sessions (e.g. clinical testing, muscle strength testing, and assessment of corticospinal and spinal excitability). For Cohort 2, when the subject receives different types of training during each of the 18 sessions, the training may comprise a total of 10 to 40-minutes of different types of walking. Depending on the gait training strategy being tested during the session, the session may comprise one or more of the following:

- Treadmill walking at a range of walking speeds (ranging from slower than comfortable self-selected speed to the subject's fast walking speed)
- Electrical stimulation applied to the ankle muscles at appropriate phases of the gait cycle during gait training
- Walking with both treadmill belts running at different speeds or directions
- Greater versus smaller dose of walking practice (three versus six 6-minute bouts)
- Bio-feedback, visual cues, or verbal / tactile cues regarding specific parameters of gait such as push-off forces, knee flexion angle during swing phase, etc.

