Subjects will not be anonymous to the researchers. As a first step during data management, subject identities will be de-identified by assigning each subject a number. Any computer files containing information that link the identifiable subject data with the de-identified subject number will be password protected and stored on a secure Emory University computer. Only de-identified data will be used to compile spreadsheets of the various outcome measures collected as part of this study (joint angles, clinical impairment scores, EMG, etc.). De-identified data may be stored for future use until 5-years after completion of the study. All signed consent forms will be stored in the subject's folder (organized by de-identified subject numbers) in a locked file cabinet at the University. Participants will not be audiotaped, photographed or videotaped without their permission during this study.

6. Participant selection

We plan to collect data on a sample of 55 individuals post-stroke and 35 able-bodied individuals. However, we anticipate a withdrawal rate of ~10%. Therefore, we will recruit 60 subjects and 45 able-bodied subjects.

Inclusion Criteria for Post-Stroke Subjects are: 1) age 30-80 years, 2) chronic stroke (>6 months post stroke), 3) first (single) lesion, 4) ambulatory with or without the use of a cane or walker, 5) sufficient cardiovascular health and ankle stability to walk for 6 minutes at their self-selected speed without an orthoses, 6) resting heart rate 40-100 beats per minute, 7) resting blood pressure between 90/60-70/90.

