Exclusion Criteria for Post-Stroke Subjects are: 1) evidence of moderate/ severe chronic white matter disease or cerebellar stroke on MRI, 2) cerebellar signs (ataxic ("drunken") gait or decreased coordination during rapid alternating hand or foot movements, 3) insulin dependent diabetes, 4) history of lower extremity joint replacement, 5) score of >1 on question 1b and >0 on question 1c on NIH Stroke Scale, 6) inability to communicate with investigators, 7) neglect/hemianopia, or unexplained dizziness in last 6 months, 8) neurologic conditions other than stroke, 9) orthopedic problems in the lower limbs or spine (or other medical conditions) that limit walking. Additional exclusion criteria for TMS (measurement of corticospinal excitability) are: 10) history of seizures, 11) metal implants in the head or face, 12) history of recurring or severe headaches/migraine, 13) headache within the past 24 hours, 14) presence of skull abnormalities or fractures, 15) hemorrhagic stroke, 16) history of dizziness, syncope, nausea, or loss of consciousness in the past 12 months.

Inclusion Criteria for Able-Bodied Individuals are: 1) age 21 to 80 years, 2) no history of neurologic disease, 3) no history of orthopedic disease or injury affecting the lower extremity.

Exclusion Criteria for Able-Bodied Individuals are: 1) history of neurologic disease, 2) history of orthopedic disease or injury to the lower extremity, 3) an implanted cardiac pacemaker. Additional exclusion criteria for the TMS portion of the study (corticospinal excitability measurement) are: 4) history of seizures, 5) metal implants in the head or face, 6) history of recurring or severe headaches/migraine, 7) headache within the past 24 hours, 8) presence of skull abnormalities or fractures.

Subject Recruitment. Study participants will be recruited from the general community within and outside Emory University.

Withdrawal from study. Participation in the present study will be voluntary and subjects will be able to opt out of the study at any time.

Our subject population will be representative of adult patients with stroke and healthy adults. The incidence of stroke is considered rare in children, estimated to be less than 13 cases per 100,000 children⁸⁸ and their inclusion would not provide additional information compared with the data gathered in adults.

7. Statistical analysis

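### H1's before/after test uses neither participants without a final test nor the intermediate evaluations; if poorer early responders withdraw, the mean change is modestly overstated

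*Combined protocol and SAP*

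**What the plan says.** Section 7 (Statistical analysis) specifies for H1 that "one-way repeated measures ANOVA will be performed to check for differences in the variable after versus before 18 sessions of training". It names no analysis set and no method for missing values. For H2 the same section plots each variable against test session and compares time to plateau and threshold time for peak propulsion, peak TMS response and overground speed.

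On data collection, section 2 promises systematic measurement of biomechanics, corticomotor excitability and walking function over the 18 Cohort 1 sessions. Section 5, item 4 (Procedures for Gait Training Sessions) is looser: "outcome measures may be obtained before, after, and intermittently throughout the 6-weeks of training". No session numbers are fixed.

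On loss, section 6 (Participant selection) states "we anticipate a withdrawal rate of ~10" per cent, a study-wide figure met by recruiting more people, and "subjects will be able to opt out of the study at any time". Section 4 puts 25 participants, stroke and able-bodied together, in Cohort 1.

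On size, the study is "powered using the primary outcome measure of paretic propulsive force generation". The claim in section 7 is that "for each aim, a sample of 24 subjects will provide 80% power". The effect assumed there is a change of 4.2 per cent in propulsive force, with an SD of 6 per cent and a two-sided test at 0.05.

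**The concern.** A repeated measures ANOVA on two time points is a paired t-test (F = t²) and needs both values from each person. Anyone who leaves before the final test is therefore dropped, including any earlier response already measured. Recruiting replacements restores the number analysed but does not correct for who was lost.

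If people who see little early gain are more likely to stop an 18-session programme, the remaining participants' mean change is too high. Section 5, item 4 says that Cohort 1 data will feed sample-size estimation for a larger trial. An inflated change there would make that trial too small. H2 already requires intermediate values for propulsion, the outcome used for power, so the information that could reduce this bias should exist for that outcome.

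**Working it through.** **1. The plan's own figure.** Inputs from section 7: difference 4.2, SD 6, two-sided alpha 0.05, power 80%, n = 24. Reading 6 as the SD of the change, d = 4.2/6 = 0.70.
- Normal approximation: ((1.960 + 0.842)/0.70)² = 16.02, so 17.
- Paired t-test (noncentral t): 19. At n = 24 the power is 90.7%.

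The stated 24 at 80% is not recovered on this reading. It is recovered if 6 is a per-session SD and the correlation is about 0.32, giving an SD of change of 6 × √(2 × (1 − 0.32)) = 7.0. The plan does not say which SD it means. Both readings are carried into step 2.

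**2. Does losing 10% cost much power?** 25 × 0.90 = 22.5, so 22 to 23 completers.
- SD of change 6: power 88 to 89%, against 92% with all 25.
- SD of change 7.0: power 77 to 79%, against 82% with all 25.

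The loss is modest. The question is bias.

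**3. Bias under different reasons for withdrawal.** Assumptions not given in the documents: four visits with means 0, 1.4, 2.8 and 4.2, SD 6 per visit and correlation 0.5. The SD of change is then 6 × √(2 × 0.5) = 6. n = 24 and the true change is 4.2. The comparison is the completers' paired change against a likelihood analysis of all available visits, with a separate mean per visit and unstructured covariance.

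| Withdrawal | Bias at 10% lost: completers / mixed model | Bias at 20% lost: completers / mixed model |
|---|---|---|
| Completely random | 0.01 / 0.00 | 0.01 / 0.00 |
| Poor early response, observed before leaving | +0.38 / +0.02 | +0.69 / −0.01 |
| Poor final response, never observed | +0.77 / +0.54 | +1.41 / +1.02 |
| Poor early response, leaving before any intermediate visit | +0.40 / +0.22 | +0.67 / +0.35 |

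With no missing data the two estimates are identical. In the second row the standard errors are 1.27 (completers) and 1.28 (mixed model) at 10% lost, and 1.35 and 1.41 at 20%. The 20% column is twice the loss the protocol expects.

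**4. Sensitivity to the assumed model.** A variant used random-slope SDs of 2 or 4 and logistic dropout on early change.
- At 7.7 to 9.2% lost, the completers' mean is 4.46 to 4.54. That is 4.46/4.2 = 1.06 to 4.54/4.2 = 1.08, or 6 to 8% high.
- At 12.3 to 14.1% lost, it is 4.61 to 4.68, or 10 to 11% high. The all-visit likelihood estimate is 4.19 to 4.23.
- The second row of the table gives 0.38/4.2 = 9% at 10% lost, inside this range.
- A further run with 25 participants and about 11% lost gave completers 4.6 to 4.7 and the unstructured model 4.26 to 4.28.

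**5. Choice of covariance.** With random-slope SD 4, a model with only a participant random intercept gave 4.39 at 8% lost and 4.34 at 12% (600 runs, Monte Carlo error about 0.05). Part of the bias remains.

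**6. Scale.** The excess in step 4 runs from 4.46 − 4.2 = 0.26 to 4.68 − 4.2 = 0.48. The completers' standard error is about 6/√22.5 = 1.27, so the excess is about 0.2 to 0.4 of a standard error.

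**7. Effect on planning.** Required n varies with 1/change² at a fixed SD. Carrying forward 4.58 (the 4.2 + 0.38 of step 3) gives (4.2/4.58)² = 0.84, so n is about 16% too small. Over the range in step 4, (4.2/4.46)² = 0.89 and (4.2/4.68)² = 0.81, so n is 11 to 19% too small.

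**The case against.** Section 5 calls Cohort 1 a case series, and H1 concerns the effect of eighteen sessions. The change in people who received eighteen sessions is a defensible target; the mixed model instead estimates the change had everyone continued. This stands as a reason to state the target explicitly. It does not settle the matter, because the plan names no analysis set and the figure is meant for planning a further trial.

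The documents give no evidence that those who leave respond poorly. The number of visits and the withdrawal models are assumed, and the main illustration uses the mechanism that a likelihood model handles best. All of this stands, so the size is conditional. The 10% is also study-wide, so loss in Cohort 1 could be lower or higher.

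Two stronger readings are tempting. A reader might infer that the intermediate data are collected and then thrown away. The documents do not support that: H2 uses them, and section 5 makes their collection permissive, with no fixed schedule. A reader might also infer that a mixed model is less biased in every case and costs nothing. Steps 3 and 5 show otherwise. It gains nothing under complete data and no reduction in bias under random loss. It removes only part of the bias when withdrawal depends on unseen response, and it needs a visit schedule the plan does not yet have.

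**Conclusion.** The point holds as a low-cost improvement. As written, H1 makes no use of participants without a final test or of the intermediate evaluations. That participants without a final test are excluded follows from how the named method works; the plan does not state it.

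If withdrawal at about the expected rate is driven by poor early response, the mean change is overstated by roughly 6 to 11%. This rests on four assumed visits, an SD of change of 6 and assumed dropout models. The bias is zero if nobody withdraws or withdrawal is completely random. It is larger, and only partly corrected by the model, if withdrawal depends on the unseen final response.

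The overstatement is well under one standard error and would rarely change the H1 test. It matters mainly for the estimate passed to the next trial. The documents do not support calling H1 invalid or materially underpowered because of withdrawal.

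**What to change.** - Name the Cohort 1 evaluation sessions and the outcomes measured at each. Keep them few, because an unstructured covariance for four visits already has 4 × 5/2 = 10 parameters for about 25 people.
- For those outcomes, analyse H1 with a mixed model for repeated measures including everyone with a baseline: categorical visit, unstructured covariance (not a random intercept alone) and small-sample degrees of freedom. Report the session-18-minus-baseline contrast with its confidence interval.
- State that the target is the change had everyone completed 18 sessions.
- Keep the paired before/after analysis as a sensitivity check. Add one for withdrawal related to unseen response, for example by lowering the missing final values over a stated range. Outcomes measured only before and after stay with the paired analysis.

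Cost: revised analysis wording, a fixed evaluation schedule and slightly more analysis work. No evaluations are needed beyond those H2 already requires. Where the model helps most, its standard error is very slightly larger (1.28 against 1.27 at 10% lost). It relies on data being missing at random given the observed visits, so bias is reduced but not removed if withdrawal depends on unobserved response or precedes any intermediate visit.

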during these testing procedures, rest breaks will be provided to the subjects as needed and as requested by the subject. Please see the adjoining flowchart for a summary of the procedures that subjects in each study cohort will undergo. Subjects will not be randomized to the 2 cohorts. Assignment to the cohorts will be based on the lab/personnel and subject schedules. A subject can participate in the 2 cohorts sequentially. Also, participants in Cohort 2, when testing hypotheses comprising a repeated-measures comparison of different gait training strategies (e.g. Hypothesis 4a evaluating effect of walking speed; Hypothesis 4b comparing FastFES versus Fast), participants may cross-over between strategies within or across gait sessions.

1) Medical Clearance:

If a subject shows interest in participation in cohort 2 of the study (18 training sessions), before participation, we will obtain written medical clearance from the subject's physician (See attached Medical Clearance form). In addition, the subject will undergo clinical assessment to confirm that they are eligible for study participation.

2) Procedures for Clinical Assessment of Walking Function and Muscle Strength:

All subjects will review and sign consent forms before clinical testing. Clinical Testing will be performed by a licensed physical therapist. Clinical testing may comprise: (1) measurement of subjects' over ground self-selected (SS) walking speed (6-meter walk test); (2) over ground walking endurance measured by the distance ambulated during the 6-minute walk test; (3) assessment of gait and dynamic balance (measured using the functional gait assessment, 4-square step test, and the Berg balance score); (4) lower extremity portion of the Fugl-Meyer score⁷⁰; (5) step activity monitoring; (6) lower extremity proprioception (in which each limb segment will be flexed or extended approximately 10 degrees and the subject will be asked to identify whether the limb is moving and in what

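### H2 threshold time calls for a within-session change in over ground speed that the Cohort 1 text does not plan, and unequal test schedules could tilt the comparison toward propulsion

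*Combined protocol and SAP*

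**What the plan says.** H2 (Section 4, Hypotheses) is a claim about order: "Improvements in gait biomechanics will precede the improvements in corticospinal excitability and walking function". Section 7 tests it in three steps:

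- The plan is that "we will plot the dependent variable versus time (test session number" for each participant; which sessions are test sessions is not listed.
- Two readouts per variable are taken from those graphs, in these words: "the time to plateau and the time when the variable first shows a positive within-session change (threshold time) will be determined".
- Both readouts are then compared by a repeated measures ANOVA with three levels: over ground walking speed, the peak response to TMS, and peak propulsion.

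The measurements are described in Section 5:

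- Over ground speed belongs to clinical testing, as "over ground self-selected (SS) walking speed (6-meter walk test" (Section 5, item 2).
- For Cohort 1, "outcome measures may be obtained before, after, and intermittently throughout the 6-weeks of training" (item 4). The parallel sentence for the other cohort differs: "For cohort 2, outcome measures may be obtained before, after, and intermittently during each of the training sessions".
- The pre- and post-test that may open and close each training session consists of 30-second treadmill trials. Spinal or corticospinal testing may be added for a few of the sessions (item 4).
- "The last training bout (bout 6) may comprise 6-minutes of over ground walking" (item 4, Cohort 1).

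**The concern.** A within-session change needs two values from the same session. The text appears to supply them for propulsion at up to every session, for TMS at some sessions, and for over ground speed at none. Two consequences follow.

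First, read literally, the three-variable threshold-time comparison lacks planned data for one of its three variables.

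Second, a first positive change can be seen only when the variable is tested. If propulsion is tested at every training session and TMS at a few, TMS will on average register its first positive change later on a training-session scale, even if both respond identically. That artefact points the way H2 predicts. Section 3 presents the time course of change as the distinctive feature of the project, and Section 5, item 4 says that Cohort 1 data will inform a larger trial, so a spurious ordering could be carried forward.

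**Working it through.** **Is there a within-session pair for over ground speed in Cohort 1?** Four places could supply one.

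- Clinical testing (item 2) includes over ground speed, but for Cohort 1 it is timed across the 6 weeks, not within a session.
- The session pre- and post-test (item 4) is on the treadmill.
- Bout 6 (item 4) is over ground, but it is optional, comes last and has no counterpart at the start of the session. It gives at most one value.
- Motion analysis (item 5) allows over ground trials, but ties none to the start and end of a session.

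No available passage plans the pair.

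**How large could the schedule effect be?** The plan gives no figure for H2 times to reproduce and no schedule, so this is an illustration on assumptions.

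*Inputs from the plan:* 18 sessions; 24 subjects and alpha 0.05 (Section 7, where the sample size is set for propulsive force, not for H2).

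*Assumptions:* propulsion tested at all 18 sessions; TMS at 9 alternate sessions, at 7 sessions (1, 4, 7, 10, 13, 16, 18) or at 4 sessions (1, 6, 12, 18). Both variables have the same chance p of a positive change at each test, and tests are independent. Time is counted in training sessions. A participant with no positive change is given session 18. Two variables are compared, for which repeated measures ANOVA equals a paired t-test.

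*Choice of p:* the only effect size given is a 4.2% difference with SD 6%. If these are taken as the mean and SD of a change (an assumption, since the text says between sessions), p = Φ(4.2/6) = Φ(0.70) = 0.76. A value of 0.9 represents clearer changes.

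*Mean threshold session,* for tests at sessions s₁ to s_J: Σ s_j·p·(1−p)^(j−1) + 18·(1−p)^J. At p = 0.76:

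- every session: about 1/0.76 = 1.32
- sessions 1, 6, 12, 18: 1(0.76) + 6(0.24)(0.76) + 12(0.0576)(0.76) + 18(0.0138) = 0.760 + 1.094 + 0.525 + 0.249 = 2.63

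Identical behaviour therefore gives an apparent lag of 2.63 − 1.32 = 1.31 sessions.

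*False rejection* (simulation, 20,000 replicates, n = 24):

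| TMS schedule, with propulsion at all 18 | p = 0.76 | p = 0.9 |
|---|---|---|
| 9 alternate sessions | 13% | 5% |
| 7 of 18 | 24% | 7% |
| Sessions 1, 6, 12, 18 | 40% | 9% |
| Both variables on one common schedule | 4-5% | about 4% |

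On the unequal schedules, nearly all rejections at p = 0.76 put propulsion first; at p = 0.9 the share is about 75-85%. Less unequal schedules shrink the effect: at p = 0.76, propulsion at 9 sessions against TMS at 4 gives 18-19%, and 7 against 4 gives 9%.

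**The case against.** The strongest reply is that the protocol may intend shared evaluations. Section 4 describes the outcome evaluations as one package covering clinical tests, gait analysis and excitability. The Cohort 1 sentence in Section 5, item 4 gives clinical and corticospinal testing the same timing. Section 7 refers to test sessions, not training sessions. If all three variables are measured at the same evaluations, the tilt is gone. This reading is reasonable but nowhere explicit, and a separate sentence in item 4 allows treadmill tests more often than TMS.

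It can also be said that *within-session* is loose wording. A plot with one value per test session shows change between sessions, and on that reading over ground speed does have data. That may be so, but the definition then needs correcting.

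The flowchart and Fig. 1 are not shown in the copy reviewed and may contain a schedule or an over ground pre- and post-trial. That limits the finding to the available text.

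A reader might infer that the H2 test is bound to confirm its hypothesis, and could cite the result at p = 0.5, where false rejection runs from 29% to 89% on the same three schedules. The documents do not support that. A value of 0.5 means no tendency to improve at all, the schedules are assumed, and at p = 0.9 the effect is small.

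**Conclusion.** The concern holds in a limited form. On the available text, the threshold-time definition cannot be applied to over ground speed in Cohort 1, and nothing guarantees that the three variables share a schedule. The first statement rests on the text alone. The second becomes a bias only if propulsion is tested more often than TMS and time is counted in training sessions; its size, 13-40% at p = 0.76 and 5-9% at p = 0.9, depends on assumed schedules, independent tests and a constant p.

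Counting each variable's own tests would also remove the tilt, but equal counts would then not mark the same point in training and could not show that one change precedes another.

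It does not follow that H2 as a whole fails. Time to plateau, the other H2 readout, needs no within-session change and was not evaluated. The sample size was set on propulsive force, so H2 has no stated power, and Cohort 1 is described as a case series. This is a point to settle before analysis, not a defect of the whole plan.

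**What to change.** In Section 7:

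1. Name the Cohort 1 assessments at which propulsion, TMS response and over ground speed are all measured, and test H2 only at those.
2. Count time as the number of training sessions completed.
3. Define threshold time, for all three variables, as the first improvement from the pre-training baseline instead of a within-session change. Within-session change in propulsion can still be reported descriptively.
4. State that crossing time depends partly on the size of the change, word a positive result as having reached detectable change earlier, and label H2 exploratory.

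The cost is mainly wording. If the three measures are not already taken at the same sessions, some tests would have to be moved or added. Time resolution becomes coarser, because propulsion data from non-shared sessions drop out of H2.

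A measurement-error margin for each variable, and a test that allows for participants who never cross (for example a Friedman test with never-crossers tied last), are optional. They carry a trade-off: in a check with assumed inputs, that test rejected in 16-29% of runs when timing was equal but the final changes differed (0.8, 0.3 and 0.5 SD), and its power for a real difference in timing was 19-49%.
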